Although an older (potentially osteoporotic) subject population is of clinical relevance, the purpose of the present study is to show and define the effect of various aspects of mechanical loading signal. Our pilot data demonstrate that the proposed intervention is osteogenic in the proposed population, which will allow us to further examine these signal characteristics in detail. Ultimately, it is our view that mechanical loading interventions will be *most effective* as a preventive tool to improve peak bone mass and bone mechanical properties in adolescents and younger adults. It has been demonstrated that high levels of physical activity, especially during growth, cause improvements to bone mass and structure that persist throughout the lifespan (Barnekow-Bergqvist, 2006). The notion of maximizing peak bone mass to protect against age-associated declines in bone strength is accepted as logical and reasonable. Given the short-term benefits of the proposed loading regime that we observed in our pilot data, the subjects who participate in this longer-term research study are likely to experience clinically relevant increases in distal radius peak bone mass and mechanical properties, potentially reducing lifetime fracture risk at this site.

Women attain peak BMC and BMD at the ultra-distal radius at age 23 and 19 respectively, and attain 94% and 98% of peak BMC and BMD by age 16 (Henry, 2004). These measures remain at peak until age 40. Changes measured during the proposed study period in a population of 21-40 year old women can, therefore, be attributed to the mechanical loading intervention.

Here we focus on women only. Given the high rate of osteoporosis that this population develops later in life, this seems a well intentioned priority. We intentionally exclude women who were recently pregnant, are lactating, or who have plans to become pregnant. Pregnancy and lactation represent

altered physiologic states that are associated with increased bone turnover. We also exclude children because they have not yet reached skeletal maturity.

Recruitment:

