Volunteers will be recruited from the communities surrounding Worcester Polytechnic Institute (WPI) including announcements made electronically and in person by members of the research team. Flyers and pamphlets explaining the study will be placed in the community, and, with permission, in the waiting room of the Family Practice clinic at the University of Massachusetts Medical Center. We will work with the institutional review board at WPI to ensure that all subject recruitment materials are compliant.

Screening:

All subjects will be verbally screened for inclusion/exclusion criteria by a member of the research team prior to being invited for a screening visit. During the screening visit, the subject's height and weight will be recorded. Subjects will receive a DXA scan of their nondominant radius and only those with BMD that falls within the specified range for inclusion will participate. Subjects will then visit the Quest Diagnostics Collection Center. There, six ml blood will be drawn via standard veinpuncture and sent to a local diagnostic laboratory (Quest Diagnostics) for a full metabolic profile including measurement of TSH, estradiol levels and Vitamin D concentration (total and 25,OH D₂ and D₃). This data will be interpreted by Drs. [name] and [name]. Potential subjects who have abnormal data and do not qualify for participation will be contacted by [name], given a copy of their laboratory results, and advised to consult their primary care physician. [name] will provide each of these individuals with his own clinical interpretation of the data, so that they understand the importance of their results.

All potential subjects who qualify to participate based on their screening will be invited to participate in the study. A signature of the informed consent document is considered a subject's written affirmation that she fits the inclusion/exclusion criteria.

Group Assignment:

For each Aim, eligible subjects will be randomized to one of two loading groups: a low, or a high group (20 subjects each) by having subjects draw a sealed envelope containing the group assignment. An additional 20 subjects will be randomized to a control (observation only) group. It is not possible to blind subjects or all team members to group assignment due to the nature of the experiment (team members cannot be blinded because group assignments must be known to assign target forces). However, all data will be blinded for analysis.

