In the second analysis, we will consider the *actual* strain magnitudes achieved by each subject, (which may differ from the group assigned strain), as a continuous variable, and will set the strain magnitude for control subjects to zero. The underlying assumption in doing this is that the baseline daily activity for *all* subjects is approximately equal, and is sufficient to maintain bone homeostasis. For this analysis, all four time points will be combined into a single model to examine changes across time after the loading regime has ended, and to compare the levels of applied strain. The dependent variable is the change score (in whole radius total BMC) from baseline; the independent variables are level of strain, time (3, 6, 9, 12 months), and a random intercept term for each subject to handle collinearity within repeated measurements. As in the first analysis method, secondary outcome measures of regional BMC, fracture strength, and others, will be considered as well.

If our hypothesis is supported then strain magnitude will be a significant predictor of change in whole radius total BMC and other related variables.

Hypothesis 1b: High initial bone mass, physical activity levels, and grip strength will be associated with diminished adaptive response for a given strain magnitude.

To test this hypothesis, initial BMC, grip strength, and physical activity will be added as potential covariates for the statistical models described in Hypothesis 1a.

If our hypothesis is supported then we would expect to observe an inverse relationship (negative coefficient) between initial bone mass, physical activity, grip strength, and change in BMC per group or per unit applied strain.

Hypothesis 1c: Bone structural changes will include increases in cortical diameter and thickness, and increased trabecular bone mass near the endosteal surface.

To test this hypothesis, the following variables will be examined:

For cortical diameter and thickness: integral and cortical bone mass and bone volume, compressive and bending strength index, and cross-sectional moments of inertia (bending and torsional)

For trabecular bone: trabecular bone mass and volume, cross sectional trabecular moments of inertia

Using the methods described for testing hypothesis 1a, changes in each of the specific variables listed will be examined at each time point. Here, the primary interest is in which specific quantities show the largest strain-related change.

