If our hypothesis is supported, we would expect to observe significant strain-dependant increases in each of the variables listed for the experimental groups, but not in the control group.

Hypothesis 1d: Local regions experiencing high strain magnitudes will experience greater local increases in BMC than regions experiencing low strain magnitudes.

This hypothesis will be tested using only subjects in the experimental conditions. For each subject, all of the elements within the baseline FE model will be divided into quartiles based on actual Von Mises equivalent strain occurring within each element. Of interest for the present analysis are elements in the highest strain quartile and the lowest strain quartile. (Note that Von Mises equivalent strains always have a positive sign.) For each of these quartile groups the change in QCT voxel density for those voxels corresponding to the location of the elements will be determined. We will use a Student's t-test to compare the average voxel density change in high strain versus low strain quartiles.

If our hypothesis is supported then elements experiencing the highest Von Mises strain will have significantly greater increases in density compared to elements experiencing the lowest Von Mises strain. Our underlying assumption in using the highest and lowest quartiles is that a minimum strain threshold is required to initiate an increase in density. Therefore, including all elements in the analysis, most of which do not exceed this threshold, may make it difficult to detect a local effect, if one is present.

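### Hypothesis 1d tests the high- versus low-strain density gap in loaded women only, so a significant gap cannot by itself be attributed to loading

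*SAP*

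**What the plan says.** SAP, Hypothesis 1d, sets out four steps.

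- Analysis set: "This hypothesis will be tested using only subjects in the experimental conditions".
- Ranking: for each woman, "all of the elements within the baseline FE model will be divided into quartiles" by Von Mises equivalent strain.
- Outcome: for the highest and lowest quartiles, "the change in QCT voxel density for those voxels corresponding to the location of the elements will be determined".
- Test and criterion: a Student's t-test of high against low. The hypothesis is supported if "elements experiencing the highest Von Mises strain will have significantly greater increases in density" than the lowest-strain elements.

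The SAP does not say whether the t-test is paired, which scan supplies the FE stiffness, or how voxels are matched to elements. No unloaded bone enters the comparison.

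Elsewhere the SAP does use an unloaded reference. The group analysis for Hypothesis 1a contrasts each loading group with control, and Hypothesis 1c expects increases "for the experimental groups, but not in the control group".

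Two statements bear on bone stability. The Protocol (Rationale for this population) argues that bone mass stays at peak to age 40, so that changes "can, therefore, be attributed to the mechanical loading intervention". The SAP (Hypothesis 1a, second analysis) assumes that daily activity "is sufficient to maintain bone homeostasis".

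**The concern.** The 1d criterion is a contrast between two sets of locations in the same loaded bone, chosen by a quantity computed at baseline. It can be met without any response to loading if change, or error in measuring change, differs between those locations.

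- **Registration and partial-volume error.** If strain and density are related, the top and bottom quartiles differ in density. A small misalignment between scans then mixes each voxel with its neighbours and shifts the two quartiles in opposite directions.
- **Regression to the mean.** If FE stiffness comes from the same baseline QCT, a voxel that reads too low by chance is given too high a strain, and its density appears to rebound at follow-up. The Protocol's radiation section counts one CT per arm in each 12-month period, so no repeat baseline QCT is described that could separate ranking from outcome.

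At stake is the interpretation of 1d, the SAP's test of local adaptation within the bone. A positive result would be read as bone responding where it was strained. Hypotheses 1a and 1c do involve controls, but for other outcomes, and they do not correct this contrast.

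**Working it through.** The plan gives no power, alpha or effect size for 1d, so there is no figure of its own to reproduce. Inputs from the Protocol are 40 loaded women per Aim (2 groups x 20), 20 controls, and CT of both arms. Everything else below is assumed.

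**1. Is unloaded bone already scanned?** The Protocol's dose for the first 12 months is 20.45 mrem. With both arms scanned: 0.05 + 2 x 9 + 4 x 2 x 0.3 = 0.05 + 18 + 2.4 = 20.45. With HR-pQCT of one arm only it would be 0.05 + 18 + 1.2 = 19.25. The stated total therefore matches both arms. The Potential Benefits section refers to a loaded arm, which implies a non-loaded one.

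**2. Noise route, no true change.** Voxel noise is 5% at each scan, divided by the square root of k for k voxels per element. Log strain = N(0, s) - b x log(observed baseline density). The result is the top-minus-bottom quartile change as a percentage of mean density.

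| Setting | Gap |
|---|---|
| b = 1, k = 1 (density log-SD 0.3 to 0.8, s 0.5 to 1.0) | 0.4 to 1.0% |
| b = 1, k = 8 | 0.06 to 0.13% |
| b = 1, k = 27 | 0.02 to 0.04% |
| b = 0 (no coupling) | -0.02 to 0.05%, about 0 |
| b = 1, k = 1, ranking from a separate scan | 0.00% |
| b = -0.5, k = 1 (log-SD 0.3, s = 0.5) | -0.6% |
| b = -1, k = 1 (same) | -1.1% |

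The last two rows take strain to rise with density. The gap then runs against the hypothesis.

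**3. Registration route, no noise and no true change.** A smooth random density field (log-SD 0.3, s = 0.5, b = 1) is shifted by one voxel. For adjacent-voxel correlation 0.94, 0.98 and 0.996 the gap is 2.4%, 0.6% and 0.16% at k = 1, and 1.6%, 0.6% and 0.15% at k = 27. A half-voxel shift gives about a quarter of the k = 1 values. With b = 0 the gap is 0 within simulation error. Ranking from a separate scan closes the noise route but not this one.

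**4. What a spurious gap does to the test.** What counts is the gap divided by its between-woman SD. For a paired (one-sample) t-test with n = 40 and two-sided alpha 0.05 (assumed), the noncentrality is (gap/SD) x sqrt(40). The last column is an unpaired t-test when a woman's two quartile means correlate 0.5.

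| Gap/SD | Paired: called significant | Unpaired |
|---|---|---|
| 0.1 | 9.5% | about 2% |
| 0.25 | 34% | about 12% |
| 0.5 | 87% | about 63% |

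The documents give no between-woman SD, so the percentages in steps 2 and 3 cannot be converted into these rows.

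**5. Precision of an unloaded reference, relative to the within-loaded test.**

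- Opposite arm, paired: SE ratio = sqrt(2(1 - r)) = 1.18, 1.00 or 0.77 at between-arm correlation r = 0.3, 0.5 or 0.7. A gap of 0.454 SD, which has 80% power within 40 loaded women, then has 66%, 80% or 95% power.
- Controls: SE ratio = sqrt(1/40 + 1/20) / sqrt(1/40) = 1.73, with 37% power for the same gap.

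**6. Does the reference remove the artefact?** With the same spurious gap in both arms (0 to 0.5 SD, r from 0.3 to 0.7), the paired arm comparison rejects in 4.9 to 5.3% of 20,000 simulated trials.

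**The case against.** The strongest reply is that 1d already has an internal reference. Its question is within the bone: do high-strain regions gain more than low-strain regions? The low-strain quartile serves as comparator, and any change common to both quartiles cancels. Leaving controls out is understandable because they have no applied strain to rank. The Protocol and SAP also argue that bone at this site is stable in these women.

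Part of this stands. The within-bone contrast is a legitimate estimand, so 1d need not be replaced, and the stability argument weakens an explanation by true drift. But cancellation covers only what the two quartiles share, and the stability statements concern average bone mass and activity, not voxel-level error that depends on density or location. Controls and opposite arms can still be ranked by running the FE model at a nominal load.

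A second objection is that the size is unknown and the direction open. That stands in full. Both simulated routes need strain-density coupling, the noise route also needs FE stiffness from the same QCT, and reversing the coupling reverses the sign. No simulated gap is tied to a between-woman SD, and the rates of 9.5%, 34% and 87% assume a paired test that the SAP does not specify.

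A reader might therefore infer that 1d is biased towards a positive result, or that its false-positive rate is known to be high. The documents support neither. A reader might also infer that the loaded-minus-opposite-arm difference should become the 1d test. That trade is debatable: the comparison is not randomised, assumes no cross-arm or dominance effect, and loses power if the arms correlate below 0.5.

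**Conclusion.** The concern holds as a limit on interpretation. As written, a significant 1d result shows that density change differs between high- and low-strain locations in loaded women. It does not show that loading caused the difference, because no unloaded bone is put through the same contrast. This follows from the SAP's text and does not depend on the simulations.

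The simulations show only that a gap without loading is possible. With strain falling as density rises, they give from 0.02% of mean density (noise averaged over 27 voxels) to 2.4% (a one-voxel shift in the least smooth field). The sign reverses under the opposite coupling, and the gap is about 0 with none. These figures rest on assumed noise, coupling, element size and smoothness, so the actual size and direction remain unknown.

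The point does not reach the primary analysis of 12-month change in whole radius total BMC, which compares loading groups with control. It should be fixed because the remedy is cheap and 1d otherwise cannot carry the claim it was written for.

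**What to change.** Amend SAP, Hypothesis 1d, as follows.

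1. State which scan builds the FE model and how voxels are matched to elements.
2. Compute one high-minus-low quartile density change per woman and arm. Keep the within-loaded comparison as the 1d test, as a paired (one-sample) t-test with the woman as the unit.
3. Run the same FE load case at a nominal load, with the same quartile split, on the non-loaded arm and in the 20 control women. Report the loaded-minus-unloaded difference with its 95% CI as a pre-specified supportive analysis.
4. Attribute the 1d gap to loading only if it exceeds the gap in unloaded bone, and define in advance what counts as exceeding it. Otherwise report a location difference.

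**Cost.** Extra FE runs on scans already planned, plus SAP wording; no new subjects or radiation. The attribution step can be less precise than the 1d test: against the opposite arm its SE is larger if the between-arm correlation is below 0.5 and smaller above it, and against controls it is always larger (1.73 times).

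**Assumptions to state.** The arm reference assumes that loading one arm does not affect the other, that arm dominance does not alter the contrast, and that strain rank does not depend on load size. The documents do not say which arm is loaded; the Protocol's Screening section says only "Subjects will receive a DXA scan of their nondominant radius". If it is always the same side, the controls' between-arm difference can check dominance, but only to about t(0.975, 19)/sqrt(20) = 0.47 SD either way. Controls are randomised and avoid the first two assumptions, at the price of precision.

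### Hypothesis 1d compares two strain quartiles from the same women by an unqualified Student's t-test; neither pairing nor the unit of analysis is stated

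*SAP*

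**What the plan says.** The SAP, under Hypothesis 1d, limits the analysis to loaded women: "This hypothesis will be tested using only subjects in the experimental conditions". The quartiles are formed within each woman: "For each subject, all of the elements within the baseline FE model will be divided into quartiles", ranked by Von Mises equivalent strain. Only the highest and lowest quartiles are used. The outcome is derived by quartile: "For each of these quartile groups the change in QCT voxel density for those voxels corresponding to the location of the elements will be determined". The test is a Student's "t-test to compare the average voxel density change in high strain versus low strain quartiles". The expected result is then put in terms of elements: "elements experiencing the highest Von Mises strain will have significantly greater increases in density".

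The words paired, unpaired and two-sample do not appear, and no unit of analysis is named. The SAP's one explicit provision for within-subject correlation is in the longitudinal model of Hypothesis 1a, which has "a random intercept term for each subject to handle collinearity within repeated measurements". It is not carried over to Hypothesis 1d.

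The Protocol, under Group Assignment, randomizes loaded subjects in each Aim to "a low, or a high group (20 subjects each"), which makes 40 loaded women per Aim. The SAP states that the analysis plan is the same for both experiments, so the point applies to each.

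**The concern.** Every loaded woman supplies both a high-strain and a low-strain value from the same scans. Anything that moves her whole scan, such as a calibration shift or a generally strong or weak response, enters both values and cancels in their difference. That cancellation is the main statistical advantage of a within-woman comparison. A two-sample t-test does not use it.

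The name Student's t-test, with nothing added, is commonly read as the two-sample form. The SAP also speaks of elements when it describes a supportive result, so an analyst could take elements or voxels as the sample. These two readings err in opposite directions. With positive correlation, the first can miss a real local effect. The second can declare one that is not there. The choice that decides Hypothesis 1d is therefore not fixed in advance.

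**Working it through.** **The plan's own figures.** There are none to reproduce. The documents give no alpha, effect size, SD, within-woman correlation or voxel count for Hypothesis 1d.

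**Inputs**
- From the Protocol: n = 2 × 20 = 40 loaded women per Aim, if all contribute.
- Assumed: two-sided alpha 0.05; equal SD σ in the two quartiles; correlation ρ between a woman's two quartile means; a true gap of 0.4σ for power.

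**Reading A: two-sample test on per-woman means**

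True variance of the mean difference = 2σ²(1 − ρ)/n. The two-sample test uses 2σ²/n. The ratio of the SE used to the true SE is therefore 1/√(1 − ρ).

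- ρ = 0.3: 1/√0.7 = 1.20
- ρ = 0.5: 1/√0.5 = 1.41
- ρ = 0.7: 1/√0.3 = 1.83

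With σ = 1 and n = 40, the two-sample SE is √(2/40) = 0.224 at every ρ. The true SE is 0.187, 0.158 and 0.122 at these three correlations.

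Type I error and two-sample power below are simulated (at least 20,000 trials per setting). Paired power is from the noncentral t with 39 df and noncentrality 0.4√40/√(2(1 − ρ)).

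| ρ | Type I error, two-sample | Power, two-sample | Power, paired |
|---|---|---|---|
| −0.3 | 8.6–8.8% | 43% | 33% |
| 0 | 5.0% | 43% | 41% |
| 0.3 | 2.0% | 41% | 55% |
| 0.5 | 0.7% | 39% | 69% |
| 0.7 | 0.06% | 37% | 89% |

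Two-sample power varies by about one percentage point between simulation runs. At ρ = 0 the two tests nearly agree. If ρ is negative, the two-sample test rejects too often, and its apparent power advantage in that row comes from the inflated type I error.

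**Reading B: voxels or elements as the unit**

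Further assumptions: m voxels per quartile per woman; a woman-level SD equal to a fraction s of the voxel SD (voxel SD = 1); ρ is now the correlation between a woman's two quartile effects.

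True variance = 2[s²(1 − ρ) + 1/m]/n. The naive variance is about 2/(nm). True SE over naive SE is about √(1 + m s²(1 − ρ)), and type I error is 2[1 − Φ(1.96/ratio)].

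At ρ = 0.5:
- m = 1,000, s = 0.05: √(1 + 1,000 × 0.0025 × 0.5) = √2.25 = 1.50; type I error 19%.
- m = 5,000, s = 0.20: √(1 + 5,000 × 0.04 × 0.5) = √101 = 10.05; type I error 84%.

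Over the same m and s, the range is 14–80% at ρ = 0.7. At ρ = 1 the woman effect cancels completely and type I error is about 5%.

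**Reading C: paired test on one difference per woman**

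Simulated type I error is between 4.7% and 5.2% for every ρ examined from −0.3 to 0.9.

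**The case against.** The strongest reply is that the SAP contains no error here, only an omission. It never says unpaired, and a paired t-test is also a Student's t-test. Quartiles are formed subject by subject and the compared quantity is an average, both of which suit one mean per woman per quartile and a paired comparison. The Hypothesis 1a model shows that the authors know repeated values from one subject are correlated. The element wording describes the expected result and is not part of the test sentence.

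Most of this stands. A reader might infer that the plan ignores the pairing, or that the p-value for Hypothesis 1d must be wrong whichever way the test is run. The documents do not support either inference, because Reading C is open to the analyst and valid. A reader might also take the voxel reading as the plan's intention and quote error rates of up to 89%. That range (29–89% for the same m and s) requires a woman's two quartile effects to be uncorrelated, which contradicts the reason for pairing in the first place.

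The reply does not show that Reading C was specified. The test sentence compares quartile groups with an unqualified test, and nothing elsewhere in the SAP or Protocol settles pairing or unit. The Hypothesis 1a random intercept belongs to a different model.

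**Conclusion.** The point holds as a gap in specification with a better method readily available. The data for Hypothesis 1d are matched by design, and the SAP names a test without saying that it uses the matching or that the woman is the unit. Of the three readings, one is valid and two generally give a wrong standard error.

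On the ordinary two-sample reading, the cost at correlations of 0.3 to 0.7 is an SE 1.20 to 1.83 times too large and a loss of roughly 14 to 52 percentage points of power for a 0.4 SD gap (55 − 41 and 89 − 37). Describing that test as conservative depends on a positive correlation. This is plausible because the scans and the woman's response are shared, but the documents do not give it. The voxel reading is less likely on the text. It is anti-conservative unless the woman effect is fully shared by both quartiles.

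The correlations, alpha, effect size, voxel counts and woman-level SDs are all assumptions. The figure of 40 is the planned number, and dropout would lower it. Hypothesis 1d is not the primary analysis: the SAP's primary dependent variable, 12-month change in whole radius total BMC by group, is unaffected. The change should be made, but the main result does not depend on it.

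**What to change.** Replace the test sentence under Hypothesis 1d with wording such as: for each loaded woman, compute the mean voxel density change in her highest-strain quartile minus that in her lowest-strain quartile; test whether the mean of these differences is zero with a paired t-test, the woman being the unit of analysis (n = 40 per Aim, 39 df if all contribute), and report the mean difference with its 95% CI. Reword the expected result so that it refers to the mean within-woman difference and not to elements.

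The cost is one or two sentences in the SAP, with no new data. If the correlation proves to be zero, the paired test loses only one or two percentage points of power (41% against 43% in the table).
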